## 7.0 TRIAL PROCEDURES

### 7.1 Trial Procedures

The Trial Flow Chart summarizes selected trial procedures to be performed at each visit. Individual trial procedures are described in detail below. It may be necessary to perform these procedures at unscheduled time points if deemed clinically necessary by the investigator.

Furthermore, additional evaluations/testing may be deemed necessary by the Sponsor and/or Merck for reasons related to participant safety. In some cases, such evaluation/testing may be potentially sensitive in nature (e.g., HIV, Hepatitis C, etc.), and thus local regulations may require that additional informed consent be obtained from the participant. In these cases, such evaluations/testing will be performed in accordance with those regulations.

#### 7.1.1 Administrative Procedures

##### 7.1.1.1 Informed Consent

The Investigator must obtain documented consent from each potential participant prior to participating in a clinical trial.

Consent must be documented by the participant's dated signature or by the participant's legally acceptable representative's dated signature on a consent form along with the dated signature of the person conducting the consent discussion.

A copy of the signed and dated consent form should be given to the participant before participation in the trial.

The initial informed consent form, any subsequent revised written informed consent form and any written information provided to the participant must receive the IRB/ERC's approval/favorable opinion in advance of use. The participant or his/her legally acceptable representative should be informed in a timely manner if new information becomes available that may be relevant to the participant's willingness to continue participation in the trial. The communication of this information will be provided and documented via a revised consent form or addendum to the original consent form that captures the participant's dated signature or by the participant's legally acceptable representative's dated signature.

Specifics about a trial and the trial population will be added to the consent form template at the protocol level.

The informed consent will adhere to IRB/ERC requirements, applicable laws and regulations and Sponsor requirements.

### **7.1.1.2 Inclusion/Exclusion Criteria**

All inclusion and exclusion criteria will be reviewed by the investigator or qualified designee to ensure that the participant qualifies for the trial.

### **7.1.1.3 Medical History**

A medical history will be obtained by the investigator or qualified designee. Medical history will include all active conditions, and any condition diagnosed within the prior 10 years that are considered to be clinically significant by the Investigator. Details regarding the disease for which the participant has enrolled in this study will be recorded separately and not listed as medical history.

### **7.1.1.4 Prior and Concomitant Medications Review**

#### **7.1.1.4.1 Prior Medications**

The investigator or qualified designee will review prior medication use, including any protocol-specified washout requirement, and record prior medication taken by the participant within 28 days before starting the trial. Treatment for the disease for which the participant has enrolled in this study will be recorded separately and not listed as a prior medication.

#### **7.1.1.4.2 Concomitant Medications**

The investigator or qualified designee will record medication, if any, taken by the participant during the trial. All medications related to reportable SAEs and ECIs should be recorded as defined in Section 7.2.

### **7.1.1.5 Disease Details and Treatments**

#### **7.1.1.5.1 Disease Details**

The investigator or qualified designee will obtain prior and current details regarding disease status.

#### **7.1.1.5.2 Prior Treatment Details**

The investigator or qualified designee will review all prior cancer treatments including systemic treatments, radiation and surgeries.

#### **7.1.1.5.3 Subsequent Anti-Cancer Therapy Status**

The investigator or qualified designee will review all new anti-neoplastic therapy initiated after the last dose of trial treatment. If a participant initiates a new anti-cancer therapy within 30 days after the last dose of trial treatment, the 30-day Safety Follow-up visit must occur before the first dose of the new therapy. Once new anti-cancer therapy has been initiated the participant will move into survival follow-up.

## 7.1.2 Clinical Procedures/Assessments

### 7.1.2.1 Adverse Event (AE) Monitoring

The investigator or qualified designee will assess each participant to evaluate for potential new or worsening AEs as specified in the Trial Flow Chart and more frequently if clinically indicated. Adverse experiences will be graded and recorded throughout the study and during the follow-up period according to NCI CTCAE Version 4.0 (see Appendix). Toxicities will be characterized in terms regarding seriousness, causality, toxicity grading, and action taken with regard to trial treatment.

Please refer to section 7.2 for detailed information regarding the assessment and recording of AEs.

### 7.1.2.2 Full Physical Exam

The investigator or qualified designee will perform a complete physical exam during the screening period. Clinically significant abnormal findings should be recorded as medical history. A full physical exam should be performed during screening,

### 7.1.2.3 Directed Physical Exam

For cycles that do not require a full physical exam per the Trial Flow Chart, the investigator or qualified designee will perform a directed physical exam as clinically indicated prior to trial treatment administration.

### 7.1.2.4 Vital Signs

The investigator or qualified designee will take vital signs at screening, prior to the administration of each dose of trial treatment and at treatment discontinuation as specified in the Trial Flow Chart. Vital signs should include temperature, pulse, respiratory rate, weight and blood pressure. Height will be measured at screening only.

### 7.1.2.5 Eastern Cooperative Oncology Group (ECOG) Performance Scale

The investigator or qualified designee will assess ECOG status (see Appendix) at each clinic visit, as specified in the Trial Flow Chart.

### 7.1.2.6 Tumor Imaging and Assessment of Disease

Except where PET/CT is indicated based on the Study Flow Chart, computed tomography (CT) is the preferred tumor imaging. For the abdomen and pelvis, contrast-enhanced magnetic resonance imaging (MRI) may be used when CT with iodinated contrast is contraindicated, or when local practice mandates it. MRI is the strongly preferred modality for imaging the brain. The same imaging technique regarding modality, ideally the same scanner, and the use of contrast should be used in a participant throughout the study to optimize the reproducibility of the assessment of existing and new tumor burden and improve the accuracy of the assessment of response or progression based on imaging.

Brain imaging is required for all participants at screening. MRI is preferred; however, CT imaging will be acceptable, if MRI is medically contraindicated.

Participant eligibility will be determined using local assessment (Investigator assessment) based on RECIST 1.1. In addition, images (including via other modalities) that are obtained at an unscheduled time point to determine disease progression, as well as imaging obtained for other reasons, but which demonstrate radiologic progression, should also be used to determine progression.

When the Investigator identifies radiographic progression per RECIST 1.1, efforts should be made to verify radiologic PD. Treatment should continue until PD has been verified. Regardless of whether PD is verified, if the Investigator considers the participant has progressed, but elects to implement iRECIST, the Investigator will assess for confirmation of progression by iRECIST at subsequent time points.

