#### **7.1.2.6.3 RECIST 1.1 Assessment of Disease**

RECIST 1.1 will be used as the primary measure for assessment of tumor response, date of disease progression, and as a basis for all protocol guidelines related to disease status (e.g., discontinuation of study treatment). Although RECIST 1.1 references a maximum of 5 target lesions in total and 2 per organ, the Sponsor allows a maximum of 10 target lesions in total and 5 per organ, if clinically relevant to enable a broader sampling of tumor burden.

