#### **7.1.2.6.4 iRECIST Assessment of Disease**

iRECIST is based on RECIST 1.1, but adapted to account for the unique tumor response seen with immunotherapeutic drugs. When clinically stable, participants should not be discontinued until progression is confirmed by the Investigator, working with local radiology, according to the rules below. This allowance to continue treatment despite initial radiologic PD takes into account the observation that some participants can have a transient tumor flare in the first few months after the start of immunotherapy, and then experience subsequent disease response.

[figure not shown]
A description of the adaptations and iRECIST process is provided in the Appendix, with additional detail in the iRECIST publication[47]. iRECIST will be used by the Investigator to assess tumor response and progression, and make treatment decisions.

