## Imaging and Treatment after First Radiologic Evidence of Progressive Disease

	Clinically Stable		Clinically Unstable	
	Imaging	Treatment	Imaging	Treatment
First radiologic evidence of PD by RECIST 1.1	Repeat imaging at 4 to 8 weeks to confirm PD.	May continue study treatment at the Investigator's discretion while awaiting confirmatory tumor imaging by site by iRECIST.	Repeat imaging at 4 to 8 weeks to confirm PD per Investigator's discretion only.	Discontinue treatment
Repeat tumor imaging confirms PD (iCPD) by iRECIST per Investigator assessment	No additional imaging required.	Discontinue treatment (exception is possible upon consultation with Sponsor).	No additional imaging required.	Not applicable
Repeat tumor imaging shows iUPD by iRECIST per Investigator assessment	Repeat imaging at 4 to 8 weeks to confirm PD. May occur at next regularly scheduled imaging visit.	Continue study treatment at the Investigator's discretion.	Repeat imaging at 4 to 8 weeks to confirm PD per Investigator's discretion only.	Discontinue treatment
Repeat tumor imaging shows iSD, iPR, or iCR by iRECIST per Investigator assessment.	Continue regularly scheduled imaging assessments.	Continue study treatment at the Investigator's discretion.	Continue regularly scheduled imaging assessments.	May restart study treatment if condition has improved and/or clinically stable per Investigator's discretion. Next tumor image should occur according to the regular imaging schedule.

iCPD = iRECIST confirmed progressive disease; iCR = iRECIST complete response; iRECIST = modified Response Evaluation Criteria in Solid Tumors 1.1 for immune-based therapeutics; iSD = iRECIST stable disease; iUPD = iRECIST unconfirmed progressive disease; PD = progressive disease; RECIST 1.1 = Response Evaluation Criteria in Solid Tumors 1.1.

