### *Assessment and Decision at RECIST 1.1 Progression*

In participants who show evidence of radiological PD by RECIST 1.1 the Investigator will decide whether to continue a participant on study treatment until repeat imaging is obtained (using iRECIST for participant management (see Table 5 and Figures 1 and 3). This decision by the Investigator should be based on the participant's overall clinical condition.

Clinical stability is defined as the following:

- Absence of symptoms and signs indicating clinically significant progression of disease
- No decline in ECOG performance status
- No requirements for intensified management, including increased analgesia, radiation, or other palliative care

Any participant deemed clinically unstable should be discontinued from study treatment at site-assessed first radiologic evidence of PD, and is not required to have repeat tumor imaging for confirmation of PD by iRECIST.

If the Investigator decides to continue treatment, the participant may continue to receive study treatment and the tumor assessment should be repeated 4 to 8 weeks later to confirm PD by iRECIST, per Investigator assessment. I

Tumor flare may manifest as any factor causing radiographic progression per RECIST 1.1, including:

- Increase in the sum of diameters of target lesion(s) identified at baseline to  $\geq 20\%$  and  $\geq 5$  mm from nadir
  - Please note: the iRECIST publication uses the terminology "sum of measurements", but "sum of diameters" will be used in this protocol, consistent with the original RECIST 1.1 terminology.
- Unequivocal progression of non-target lesion(s) identified at baseline
- Development of new lesion(s)

iRECIST defines new response categories, including iUPD (unconfirmed progressive disease) and iCPD (confirmed progressive disease). For purposes of iRECIST assessment, the first visit showing progression according to RECIST 1.1 will be assigned a visit (overall) response of iUPD, regardless of which factors caused the progression.

At this visit, target and non-target lesions identified at baseline by RECIST 1.1 will be assessed as usual.

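### Section 7.1.2.6 continues treatment until progression is verified, while the table after 7.1.2.6.4 and Appendix 4 stop it at first radiologic progression in clinically unstable participants; nothing says which prevails

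*Combined protocol and SAP*

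**What the plan says.** The opening text of Section 7.1.2.6 sets a general rule. The trigger is: "When the Investigator identifies radiographic progression per RECIST 1.1, efforts should be made to verify radiologic PD". The instruction that follows is: "Treatment should continue until PD has been verified". Clinical condition is not mentioned. The next sentence begins "Regardless of whether PD is verified, if the Investigator considers the participant has progressed, but elects to implement iRECIST" and goes on to have the investigator look for iRECIST confirmation at later time points.

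The table after Section 7.1.2.6.4 splits participants by clinical stability. In the row for first radiologic progression, the treatment entry for unstable participants is "Discontinue treatment", and the imaging entry is "Repeat imaging at 4 to 8 weeks to confirm PD per Investigator's discretion only". Appendix 4, under Assessment and Decision at RECIST 1.1 Progression, agrees with the table: "Any participant deemed clinically unstable should be discontinued from study treatment at site-assessed first radiologic evidence of PD". It adds that these participants need no confirmatory scan.

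The subsection Tumor Imaging During the Study lets participants with unconfirmed progression stay on treatment if the investigator chooses. It points to Section 9.2.1.6 for the iRECIST rules, for the conditions on continuing and for the exceptions to stopping.

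**The concern.** These are operative instructions to sites on whether to give the next treatment. A site that reads the opening of 7.1.2.6 and a site that reads the table or Appendix 4 could act in opposite ways on the same participant. That participant is, by the protocol's own definition of instability, someone with symptoms of progression, a falling performance status or a need for intensified management. Section 5.7 names a lead centre and three subsites, so different readings are foreseeable. At stake are participant safety and consistent timing of treatment discontinuation. Adverse-event windows counted from the end of treatment would shift with it.

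**Working it through.** No formula applies and the plan states no figure on this point. The check is a comparison of the rules.

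| Place | Who it covers | Treatment after radiologic progression |
|---|---|---|
| 7.1.2.6, opening text | Anyone with investigator-identified RECIST 1.1 progression | Continue until verified |
| Tumor Imaging During the Study | Unconfirmed progression, subject to Section 9.2.1.6 | May continue if the investigator so decides |
| 7.1.2.6.4, text | Clinically stable | Do not stop before confirmation |
| Table after 7.1.2.6.4, first progression | Clinically stable | May continue if the investigator so decides |
| Table after 7.1.2.6.4, first progression | Clinically unstable | Stop; repeat scan optional |
| Appendix 4 | Clinically unstable | Stop at the site's first reading of progression |
| 5.5 | Confirmed progression as in 7.1.2.6, or unnecessary risk | Must stop |

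1. **Clinically stable participants.** The rules differ in strength (should continue, may continue, should not be stopped) but do not point in opposite directions.

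2. **Clinically unstable participants, progression not yet verified.** The opening of 7.1.2.6 says continue. The table and Appendix 4 say stop. All three cover this participant at the same moment, so the rules are opposite here.

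3. **Does the meaning of verification remove the conflict?** The term is undefined, and 7.1.2.6 treats it as separate from iRECIST confirmation. If it means a second look at the same scan, the conflicting interval may be short. It does not vanish, because Appendix 4 acts on the site's first assessment. If it meant iRECIST confirmation, the rule would wait for a scan that unstable participants need not have. Neither reading reconciles the text.

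4. **Does any passage set precedence?** None does. Section 5.5 cites 7.1.2.6 as a whole, and both the general sentence and the table fall under that heading. Section 9.2.1.6 does not exist: Section 9.2 is one sentence on packaging and labeling, with no subsections.

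5. **Size.** The number affected would be the number of participants with a first radiologic progression, times the share clinically unstable at that point. The documents give no such share and no duration for verification. Neither the count nor the interval can be derived.

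**The case against.** The strongest reply is that 7.1.2.6 opens with a general rule and the table and Appendix 4 supply the specific one. The specific texts agree with each other, all turning on clinical stability, and a careful reader would follow them. Section 5.5 also requires stopping when the investigator or sponsor judges that continuing puts the participant at unnecessary risk, and it allows stopping for safety reasons. This has weight: a site reading the whole protocol is unlikely to treat on against clinical judgement. But the protocol nowhere says that the table overrides the opening text, and the reference that might have settled it leads nowhere. Discretion to stop for risk is a safeguard, not a reconciliation.

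A reader might also infer more than the documents support:

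- **Extra doses.** Dividing the 4 to 8 week confirmation interval by the 3-week cycle gives 4/3 = 1.3 to 8/3 = 2.7 cycles. That interval belongs to iRECIST confirmation, which 7.1.2.6 separates from verification, so it does not measure this conflict.
- **Participants affected.** From Section 8.1, 25 × (1 − 0.65) = 8.75 and 25 × (1 − 0.40) = 15 expected events within a year. These are all PFS events, deaths included, and the second uses the rate expected with standard chemoradiotherapy. Neither counts clinically unstable participants at first progression.
- **Rival criteria.** Section 7.1.2.6.3 makes RECIST 1.1 the reference for rules on disease status, stopping treatment included, while 7.1.2.6.4 says "iRECIST will be used by the Investigator to assess tumor response and progression, and make treatment decisions". With Appendix 4 this reads mostly as a sequence: RECIST 1.1 flags progression, then iRECIST governs confirmation. It is not a second contradiction of the same weight.
- **Follow-up phase.** Under Section 7.1.5.3, survival follow-up starts at confirmed progression or new anticancer therapy. Stopping treatment does not itself start it.
- **Primary endpoint.** Section 8.1 dates confirmed progression to the first scan showing it, so treating on in the meantime does not move that date.

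**Conclusion.** The contradiction stands, in a narrow form. For a clinically unstable participant with a first, not yet verified, radiologic progression, one operative passage says continue and two say stop, with no stated precedence and a dead cross-reference. This rests on reading the opening of 7.1.2.6 as an instruction to sites, which its wording and its trigger support. It does not depend on how verification is understood, although the length of the conflict does. The number of participants and the interval are unknown. The planned 25 PembroRT participants and the stated 81% power are unaffected. The point should be corrected because it concerns treatment of participants who may be deteriorating and the correction is cheap. The documents do not show that any participant would in fact be treated against clinical judgement.

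**What to change.** Reconcile the opening text of 7.1.2.6 with the table after 7.1.2.6.4 and with Appendix 4, so that one statement covers treatment at first radiologic progression for both stable and unstable participants. The sponsor and investigators decide which clinical rule that statement carries. In the same edit, define verification (who does it, on which images) and say how it relates to iRECIST confirmation. Replace each reference to Section 9.2.1.6 with the section intended.

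The cost is a text amendment touching several places, plus a note to the sites. No change to design, sample size or analysis is needed.

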#### **7.1.2.6.1 Initial Tumor Imaging**

Initial tumor imaging at Screening must be performed within 42 days prior to the date of allocation. The site study team must review screening images to confirm the participant has measurable disease per RECIST 1.1.

The screening images must be submitted to the central imaging vendor for retrospective review.

Tumor imaging performed as part of routine clinical management is acceptable for use as screening tumor imaging if they are of diagnostic quality and performed within 42 days prior to the date of allocation and can be assessed by the central imaging vendor.

Brain imaging is required to rule out radiographically detectable untreated brain metastases. Magnetic resonance imaging is preferred; however, CT imaging will be acceptable, if MRI is medically contraindicated or CT is mandated by local practice.

#### **7.1.2.6.1 Tumor Imaging During the Study**

On-study imaging assessments should be performed at the timepoints ( $\pm 7$  days) detailed in the Trial Flow Chart for each study cohort. Imaging timing should follow calendar days and should not be adjusted for delays in cycle starts. Imaging should continue to be performed until disease progression is identified by the Investigator. Once disease progression is confirmed, imaging should be performed as needed for routine clinical care and does not need to adhere to the Trial Flow Chart.

Per iRECIST (Section 9.2.1.6), disease progression should be confirmed by the site 4 to 8 weeks after first radiologic evidence of PD in clinically stable participants. Participants who have unconfirmed disease progression may continue on treatment at the discretion of the Investigator until progression is confirmed by the site provided they have met the conditions detailed in Section 9.2.1.6. Participants who receive confirmatory imaging do not need to undergo the next scheduled tumor imaging if it is less than 4 weeks later; tumor imaging may resume at the subsequent scheduled imaging time point, if clinically stable. Participants who

have confirmed disease progression by iRECIST, as assessed by the site, will discontinue study treatment. Exceptions are detailed in Section 9.2.1.6.

